8.5.1.2 Safety Assessments

Planned safety assessments include:

- Neurological and physical examinations
- Clinical laboratory tests
- 12-lead ECG
- Vital signs including temperature, blood pressure, pulse rate, respiration rate, height, weight and BMI
- AE monitoring: frequency, severity, duration, causality, outcome

Safety laboratories, vitals and ECG measurements may be repeated if needed to corroborate or refute abnormal findings. Both the original and replicate assessments should be recorded in the CRF.

See Schedule of Events for timing of Safety Assessments.

8.5.1.3 Schedule of Study Procedures

8.5.1.3.1 Visit 1 (same as Study1042-0603 Visit 10/Open Label Month 12)

1042-0603 Visit 10/Last Visit procedures: physical and neurological examination, 12-lead ECG, vital signs, blood and urine samples for safety laboratory tests and urine pregnancy test for WCBP, trough concomitant AED levels, subject diaries, C-SSRS, CGI-I, PCGI-I , AEs reviewed, medication compliance checked and study medication returned;

Additional 1042-0604 procedures: informed consent reviewed and signed; inclusion/exclusion and demographics/medical history reviewed; and 1042-0604 seizure calendars and study medication dispensed. Any Adverse Event that occurred in study 1042-0603 which is not resolved at the time of enrollment into 1042-0604 or is deemed significant by the Principal Investigator is to be captured in the subject's 1042-0604 medical history. If the frequency, severity or duration of this event changes in any way then it is to be captured as an Adverse Event in 1042-0604.

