9.5.1 Definitions

Adverse event means any untoward medical occurrence associated with the use of a drug in humans, whether or not considered drug related. An AE can therefore be any unfavorable and unintended sign (including a clinically significant abnormal laboratory finding), symptom or disease temporally associated with the use of an investigational product, whether or not considered related to the investigational product. Any worsening of a preexisting condition (i.e., any clinically significant adverse change in frequency and/or intensity) which is temporally associated with the use of the investigational product, is also an adverse event.

A serious adverse event (SAE) is any untoward medical occurrence that at any dose (including overdose) that meets one or more of the following criteria:

- Is fatal, as a direct outcome of the AE
- Is life threatening

This serious criterion applies if the subject, in the view of the Investigator, is at substantial risk of dying from the AE as it occurs. It does not apply if an AE hypothetically might have caused death if it were more severe.

- Requires or prolongs inpatient hospitalization

This serious criterion applies if the reported AE necessitates an inpatient admission (in the US) or a minimum 24-hour inpatient hospitalization (outside US) or, if in the opinion of the Investigator, prolongs an existing hospitalization. A hospitalization for an elective procedure, a routinely scheduled treatment or a social admission is not an SAE.

- Results in permanent or significant disability/incapacity

This serious criterion applies if the “disability” caused by the reported AE results in a substantial disruption of the subject’s ability to carry out normal life functions.

- Results in a congenital anomaly/birth defect

This serious criterion applies if a subject exposed to the investigational product gives birth to a child with congenital anomaly or birth defect.

Important medical events that do not meet any of the criteria above may be considered serious when, based upon appropriate medical judgment, they may jeopardize the subject and may require medical or surgical intervention to prevent one of the outcomes listed in this definition. Examples of such medical events include allergic bronchospasm requiring intensive treatment in an emergency room or at home, blood dyscrasias or convulsions

that do not result in inpatient hospitalization, or the development of drug dependency or drug abuse.

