9.5.2 Evaluating and Recording of Adverse Events

At each visit all adverse events that are observed, elicited by the Investigator, or reported by the subject, will be recorded in the appropriate section of the AE CRF and evaluated by the Investigator.

Minimum information required for each AE includes type of event, duration (start and end dates), severity, seriousness, causality to study drug, action taken, and outcome.

Severity of AEs will be graded by the Investigator using the following criteria as guidelines:

1. Mild: Nuisance, barely noticeable.
2. Moderate: Uncomfortable, troublesome symptoms not significantly interfering with daily activities or sleep.
3. Severe: Symptoms significantly interfere with daily activities or sleep.

The relationship of the AE to the study drug should be specified by the Investigator, using the following definitions:

1. Not Related: Concomitant illness, accident or event with no reasonable association with study drug.
2. Unlikely Related: The event has little or no temporal sequence from administration of the study drug, and/or a more likely alternative etiology exists.
3. Possibly Related: The event follows a reasonable temporal sequence from administration of study drug **but which could also be explained** by concurrent disease or other factors or medications.
4. Probably Related: The event follows a reasonable temporal sequence from administration of study drug, **but is unlikely to be attributed** to concurrent disease or other factors or medications. A clinically reasonable response may be observed if the study drug is withdrawn or dose reduced.
5. Definitely Related: the event follows a reasonable temporal sequence from administration of study drug and is definitive pharmacologically; cannot be attributed to concurrent disease or other factors or medications. A clinically reasonable response

should be observed if the study drug is withdrawn or dose reduced.

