7.1 ADVERSE EVENTS

Adverse events (AEs) will be coded by System Organ Class (SOC) and Preferred Term (PT) using the Medical Dictionary for Regulatory Activities (MedDRA®, version 16.0/AECODE). The verbatim term will be included in the AE listings.

A treatment-emergent adverse event (TEAE) is defined as an AE that occur or worsen on or after the first dose of study drug in Study 1042-0604 and before the end of the study (including the safety follow-up period). Only TEAEs will be included in summary tables. All AEs, treatment emergent or otherwise, will be presented in subject data listings.

The TEAEs will be summarized as the number (percentage) of subjects with TEAEs within SOC and PT. Subjects who report the same PT on multiple occasions will be counted once for the PT: under the highest severity (severe > moderate > mild) when summarized by severity and under the closest relationship (related > probably related > possibly related > unlikely related > Not related) to study drug when summarized by relationship. If a subject reports multiple PT for a SOC, the subject will be counted only once for that SOC. Treatment related AEs are defined as those events recorded on the CRF as 'Related', 'Probably Related' or 'Possibly Related', others will not be related AEs.

TEAEs will be summarized as below.

- An overview table, including number of subjects with
 - TEAEs
 - serious AEs (SAEs)
 - study drug related TEAEs
 - TEAEs by severity

- TEAEs leading to study discontinuation
- TEAEs leading to death
- TEAE by SOC and PT
- TEAE by SOC, PT, and Severity
- TEAE by PT
- TEAEs by SOC, PT, and Relationship to Study Drug

All AE tables will be sorted by SOC and PT in decreasing frequency of the number and percentage of subjects.

Missing date will be imputed followed table describes how missing date information will be handled:

Partial Missing Start or Stop Date	Imputed Start Date	Imputed Stop Date
Missing month and day, and the year is present	January 1 of that year or first dose date if the year is the same as the year of first dose date	December 31 of that year
Missing day, but year and month are present	First day of that month or first dose date if the year and month are the same as the year and month of first dose date	Last day of that month
Missing month, but year and day are present	Missing month imputed as January	Missing month imputed as December

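### Protocol 8.5.1.3.1 records any change in a carried-over event as an AE, contrary to the worsening-only rule in 9.5.1; with no onset-date rule, improvements can reach the TEAE tables

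*Protocol*

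**What the plan says.** Protocol 8.5.1.3.1 (Visit 1) deals with events inherited from the parent study. A 1042-0603 event "which is not resolved at the time of enrollment into 1042-0604 or is deemed significant by the Principal Investigator is to be captured" in the 1042-0604 medical history. The section continues: "If the frequency, severity or duration of this event changes in any way then it is to be captured as an Adverse Event" in 1042-0604. This is current text, added by Amendment 1.

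Protocol 9.5.1 sets the general rule for conditions that predate the study: "Any worsening of a preexisting condition (i.e., any clinically significant adverse change in frequency and/or intensity", when linked in time to use of the product, is an AE. Duration is not among its criteria.

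Protocol 9.5.2 lists what is recorded: "Minimum information required for each AE includes type of event, duration (start and end dates), severity, seriousness", and further items including outcome. It does not say whether a re-captured event keeps its 1042-0603 onset or takes the date of the change.

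SAP 7.1 then filters for tabulation. A TEAE is "defined as an AE that occur or worsen on or after the first dose of study drug in Study 1042-0604", up to the end of safety follow-up. "Only TEAEs will be included in summary tables". "All AEs, treatment emergent or otherwise, will be presented in subject data listings". A partial start date is set to the first dose date when its known year, or year and month, matches that date.

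**The concern.** The two protocol rules give different answers for the same event. One that eases from moderate to mild must be captured under 8.5.1.3.1, but is not an AE under the worsening clause of 9.5.1. Because 8.5.1.3.1 also names duration, and 9.5.2 describes duration by start and end dates, the end of an open event can be read as a change too.

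Inherited events are to be expected. Every subject enters already taking ganaxolone. Exclusion criterion 2 removes only serious events, and moderate or severe medically important events, that were judged probably or definitely related. Mild related events and non-serious, possibly related events can therefore be carried in. SAP 7.1 counts possibly related events as treatment related, so a re-captured event could also appear in the drug-related counts.

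Safety and tolerability is the primary objective, and the TEAE tables are a main part of the evidence for it. At stake is whether they can include events in which nothing adverse happened during 1042-0604.

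**Working it through.** The documents give no expected TEAE rate, no share of subjects with carried-over events and no power calculation, so there is no plan figure to reproduce. The check is a comparison of the rules, followed by an illustration on assumed inputs.

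**Step 1. The rules side by side, for an event that began in 1042-0603**

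| Course in 1042-0604 | Captured under 8.5.1.3.1? | AE under the 9.5.1 worsening clause? | TEAE if 1042-0603 onset is kept? | TEAE if onset is the date of change? |
|---|---|---|---|---|
| Clinically significant worsening | Yes | Yes | Yes (worsens) | Yes (occurs) |
| Improvement | Yes | No | No, listings only | Yes (occurs) |
| Resolution | Arguably, as a change in duration | No | No, listings only | Yes (occurs) |
| No change | No | No | Not captured | Not captured |

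The protocol conflict is in the second and third rows. The SAP filter repairs it in the fourth column but not in the fifth.

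**Step 2. Routes into the TEAE tables**

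1. The site enters the date of change as the start date. Nothing in Protocol 9.5.2 or SAP 7.1 forbids this, and SAP 7.1 requires no link to the medical-history entry.
2. The start date is partial. Take the first dose date in the imputation table to be the 1042-0604 one, as in the TEAE definition. An event that began earlier in the same calendar year, with only the year recorded, is then given the first dose date as its onset and counts as occurring on study. No exception is made for onsets known to predate 1042-0604.

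SAP 7.1 also does not say against what status worsening is judged.

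**Step 3. Illustrative size (all inputs assumed)**

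Let p be the share of subjects with a genuine TEAE, c the share with a carried-over event that only improves or resolves, and f the share of those events whose recorded or imputed onset falls on or after first dose. Assuming independence:

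observed share = p + (1 − p) × c × f, so excess = (1 − p) × c × f.

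| p | c | Excess, f = 0 | f = 0.5 | f = 1 |
|---|---|---|---|---|
| 50% | 5% | 0 | 1.25 points | 2.5 points |
| 50% | 20% | 0 | 5 points | 10 points |
| 60% | 20% | 0 | 4 points | 8 points (60% becomes 68%) |
| 90% | 5% | 0 | 0.25 points | 0.5 points |
| 90% | 20% | 0 | 1 point | 2 points |

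For a single preferred term, with p = 2–10%, c = 1–5% and f = 1, the excess runs from 0.90 × 1% = 0.9 points to 0.98 × 5% = 4.9 points.

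SAP section 9 reports low patient numbers without giving n. If n were 20 to 50, one wrongly counted subject would move a percentage by 1/20 = 5 points down to 1/50 = 2 points.

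**The case against.** The strongest reply is that 8.5.1.3.1 governs what goes on the case report form, not what is tabulated. SAP 7.1 applies its own test, and an event that began in 1042-0603 and then eased or ended neither occurs nor worsens in 1042-0604. A reader might infer that every improvement becomes a TEAE and inflates a primary safety result. The documents do not support that, for two reasons. With the 1042-0603 onset kept, the event goes only to the listings. And there is no single primary safety result: safety is the primary objective, reported descriptively in one arm without a hypothesis test.

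Other parts of the reply also have weight:

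- Protocol 8.5.1.2 and 9.5.2 list duration and outcome separately, so a site could record resolution as an outcome and not as a change in duration. The resolution reading is therefore arguable, while the improvement reading follows directly from the text.
- A site may read 8.5.1.3.1 together with the untoward-occurrence definition in 9.5.1. That is possible, but the more specific instruction says otherwise.
- Entry requires acceptable tolerability and follows about a year of open-label treatment, which plausibly reduces carried-over drug effects. No document supports a high value of c.
- Over-capture does not hide harm, and every AE is listed with its verbatim term.
- The study ended early, so a protocol edit alone would change little.

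These points limit the size and certainty of the effect. They do not remove the conflict between 8.5.1.3.1 and 9.5.1, and they do not supply the missing onset-date rule on which the SAP filter depends.

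**Conclusion.** The contradiction between Protocol 8.5.1.3.1 and 9.5.1 is firm and rests on current text alone. Literal use of 8.5.1.3.1 records improvement, and arguably resolution, as a 1042-0604 AE. Inflation of the TEAE tables is conditional: it needs a start date set at the change, or a partial date imputed to first dose, and neither document prevents either. This route can only add counts, so any error is upward.

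The size cannot be derived from the documents. It is zero if the 1042-0603 onset is always kept and at most c(1 − p) if every such event receives an on-study onset. The figures above illustrate that range on assumed p, c and f with independence; they are not estimates for this trial. The point deserves correction because the affected tables support the primary objective and the correction is cheap.

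**What to change.** **Protocol 8.5.1.3.1 (or the CRF completion guideline).** Use the 9.5.1 criterion: capture a carried-over event as a 1042-0604 AE only on a clinically significant adverse change in frequency or intensity. Record improvement or resolution against the medical-history entry.

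**SAP 7.1, for data already collected.** This is the step with practical effect, given the early termination.

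1. Link each 1042-0604 AE to any matching carried-over medical-history entry.
2. Keep the 1042-0603 onset date for linked events without worsening.
3. Judge worsening against the event's status at 1042-0604 Visit 1.
4. Do not impute to the first dose date any onset known to predate 1042-0604.
5. Leave non-worsening carried-over events out of the TEAE tables and keep them in the listings.

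The cost is one sentence in the protocol or guideline, one SAP derivation, and a small review of carried-over events against medical history. No data are lost, because SAP 7.1 already lists all AEs.

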8.5.1.3.2 Visit 2 (Week 17)

Concomitant AEDs reviewed, brief physical and neurological exams, vital signs, safety laboratory tests, urine pregnancy test, C-SSRS, review safety and record AEs, subject calendar review, study medication return and compliance check and dispense study medication.

8.5.1.3.3 Visit 3 (Week 34)

Concomitant AEDs reviewed, brief physical and neurological exams, vital signs, safety laboratory tests, urine pregnancy test, C-SSRS, review safety and record AEs, subject calendar review, study medication return and compliance check and dispense study medication.

8.5.1.3.4 Visit 4 (Week 52)

Concomitant AEDs reviewed, physical and neurological exams, vital signs, local ECG, safety laboratory tests, urine pregnancy test, C-SSRS, review safety and record AEs, subject calendar review, CGI-I, PCGI-I, study medication return and compliance check and dispense study medication.

8.5.1.3.5 Visit 5 (Week 69)

Concomitant AEDs reviewed, brief physical and neurological exams, vital signs, safety laboratory tests, urine pregnancy test, C-SSRS, review safety and record AEs, subject calendar review, study medication return and compliance check and dispense study medication.

8.5.1.3.6 Visit 6 (Week 86)

Concomitant AEDs reviewed, brief physical and neurological exams, vital signs, safety laboratory tests, urine pregnancy test, C-SSRS, review safety and record AEs, subject calendar review, study medication return and compliance check and dispense study medication.

8.5.1.3.7 Visit 7/Early Term Visit (Week 104; start of dose de-escalation period)

Concomitant AEDs reviewed, physical and neurological exams, vital signs, local ECG, safety laboratory tests, urine pregnancy test, C-SSRS, review safety and record AEs, subject calendar review, CGI-I, PCGI-I, study medication return and compliance check and dispense study medication.; dose de-escalation instructions given.

8.5.1.3.8 Visit 8 Safety Follow-up (Week 106; follow-up for end of dose de-escalation period)

Concomitant AEDs reviewed, brief physical and neurological exams, vital signs, safety laboratory tests, urine pregnancy test, C-SSRS, review safety and record AEs, subject calendar review and study medication return and compliance check.

8.5.1.3.9 Unscheduled Visit

Activities to be determined by the nature of the visit, are at the Investigator's discretion. In most cases basic safety procedures (vital signs, review of adverse events) should be completed.

8.6 Data Quality Assurance

Steps to be taken to assure the accuracy and reliability of safety data include the selection of qualified Investigators and appropriate study centers, review of protocol procedures with the Investigator and associated personnel prior to the study, and periodic monitoring by a Sponsor representative. Case report forms will be reviewed for accuracy and completeness by a Sponsor representative during on-site monitoring visits and after their return to the Sponsor, and any discrepancies will be resolved with the Investigator or designees, as appropriate. The data will be entered into the clinical trial database and verified for accuracy.

8.7 Statistical Methods Planned and Determination of Sample Size

8.7.1 Statistical and Analytical Plans

8.7.1.1 Randomization

This is an open-label extension study and no randomization will occur.

8.7.1.2 Analysis Populations

All subjects who sign informed consent and take one dose of study medication in this study will be included in the ITT Safety Population. Subjects who return at least 25 days of seizure calendar data will be included in the Full Analysis Population.

8.7.1.3 Analysis of Efficacy Variables

The primary outcome measure is the percentage change in seizure (POS with or without secondary generalization) frequency per 28-days relative to baseline in study 1042-0603. Results will be expressed in mean and median change.

Secondary efficacy outcome measures include proportion of subjects experiencing a $\geq 50\%$ reduction at the end of the study compared with Study 1042-0603 baseline

(proportion of Responders), seizure free intervals and seizure free days. The CGI-I and PCGI-I are also secondary efficacy assessments.

8.7.1.4 Analysis of Safety Variables

Adverse events (AEs) will be tabulated by overall, system organ class (SOC), and Preferred Term using the MedDRA v.16.0 coding system. Incidence and percentage of adverse events, by dose and overall. Additional tables, with AEs subset by severity and by relationship to drug as assessed by the investigator will be presented. Subset listings will be produced for adverse events that cause withdrawal and for SAEs.

Laboratory data, vital signs and ECGs will be summarized using descriptive statistics. Important changes in laboratory, ECG values and vital signs will be flagged in data listings. Listings of most abnormal changes will be provided.

8.7.2 Determination of Sample Size

This is an open-label, long-term continuation study. Sample size will be determined by those eligible after successful completion of Study 1042-0603.

9. INVESTIGATOR REQUIREMENTS

9.1 Study Initiation

The following documentation must be received by the Sponsor or their representative prior to initiation of the trial:

1. Completed FDA Form 1572, signed by Principal Investigator. Investigators must also complete all regulatory documentation as required by the ICH GCP and local or national regulations.
2. Current curricula vitae of the Principal Investigator, all sub-investigators and key research personnel.
3. Institutional Review Board (IRB) or Ethics Committee (EC) membership list and/or Department of Health and Human Services number.
4. The ICF must be reviewed and approved by the Sponsor or their designee.
5. Written documentation of IRB/EC approval of protocol (identified by protocol number or title and date of approval) and ICF (identified by protocol number or title and date of approval). A copy of the approved ICF must be supplied.
6. Current laboratory certification of any laboratories performing the analysis (issuing agency and expiration date), as well as current normal laboratory ranges for all laboratory tests.
7. A signed Clinical Research (Protocol) Agreement.
8. Certified translations of IRB/EC approval letters, pertinent correspondence, and approved ICF (when applicable).
9. Financial disclosure form for Principal Investigator and all sub-investigators.

9.2 Study Completion

The following data and materials are required by the Sponsor or their designee before the study can be considered complete or terminated:

1. All test results from Visit 1 through the end of the study (e.g., clinical data, all special test results).
2. Information properly recorded in the CRFs by appropriate study personnel and signed and dated by the Investigator.
3. Completed drug accountability records.
4. Copies of protocol or ICF amendments and IRB/EC approval/notification, if appropriate.
5. Copies of IRB/EC notification or approval for safety updates.
6. A summary of the study prepared by the Principal Investigator (an IRB/EC summary close letter is acceptable).

